7.1 Universal precautions and safety

Safety of study staff, food bank staff, volunteers, and clients are top study priorities. While the risk of injury and/or infections disease transmission associated with our community screening program is negligible, risk still exists. To further reduce risk and maintain a safe screening environment, all study staff, food bank personnel, and food bank volunteers who conduct screening and testing activities will complete training on universal precautions and screening safety (or demonstrate evidence that they successfully participated in a comparable training program) prior to screening clients. Training will include information on: hand hygiene, proper use of personal protective equipment (e.g., nitrile gloves), surface sanitizers, single-use lancet devices, sharps containers (including use, transport, and storage), proper testing techniques with clients, and on developing site-specific sharps and accidental needle stick protocols.

7.2 Random blood sugar testing

We will use GE100 Blood Glucose Monitoring System (Bionime Corporation) glucometers to conduct all random blood glucose testing with food pantry clients and study participants. The GE100 Blood Glucose Monitoring System received U.S. FDA 510K approval for use by healthcare personnel to test multiple patients.

Random blood glucose testing can be conducted by trained study staff and food bank personnel. Testing will follow manufacturer guidelines for glucometer use, maintenance, cleaning, and quality assurance (see Glucometer User Manual in **Appendix M**).

Materials List for Random Blood Glucose Testing

- GE100 Blood Glucose Meter
- GE100 Blood Glucose Test Strip (check expiration date on strips; do not use expired strips)
- Hand sanitizer
- Nitrile gloves
- Alcohol prep pad (minimum 70% alcohol)
- Single-use lancet device
- Cotton balls
- Bandage
- Dental bib (disposable barrier)
- Surface sanitizer (Sani Cloth Super Wipes)
- Trash can with liner

- Sharps container
- Dex4 Glucose Tabs

7.2.1 Procedure to conduct a blood glucose test

1. Have client sit at health screening table.
2. Introduce yourself and provide client with background on screening.
3. Ask client: “have you ever been told by a doctor that you have diabetes?”
4. Always maintain client privacy. If necessary, ask other food bank clients to stand away from the screening area.
5. Clean hands with hand sanitizer.
6. Set up testing supplies.
7. Put on exam gloves.
8. Ask if client has a preference for which finger to use in order to access blood sample.
 - a. Do not use any site on a finger that is an open wound, has scar tissue, has evidence or infection, or has any other contraindication (e.g., previous diabetes-related amputation, scleroderma); select a different finger for testing.
9. Ask client to hang hand below table and open and close their fist 3-4 times in order to increase blood flow to the fingers.
10. Open alcohol swab and clean finger at site where sample will be obtained. The side of the finger provides a blood sample with less pain than the center of the finger pad.
11. Allow finger to air dry or blot with clean cotton ball to dry site.
12. Take one GE100 Blood Glucose Test Strip from the vial. Close the vial cap immediately.
13. Insert the test strip into Test Strip Port of the GE100 Glucose Meter with the indication symbol facing up; the meter confirms the insertion of a strip with a beep (if volume is turned on).
14. A blood drop icon will appear on the meter display window and will be accompanied by a beep (if the volume is turned on). Apply the blood sample within 2 minutes.
15. A minimum of 1.0µL of blood is needed for testing with the GE100 Blood Glucose Monitoring System. Blood sample size above 3.0µL might contaminate the test strip port and the meter. Blood sample size below 1.0µL might cause inaccurate test results or might not start the meter. In this case, repeat the test with a new test strip.
16. Place lancet device against prepared site on client’s finger and push down quickly and firmly.
17. Assess puncture site; if necessary provide light pressure around puncture site to form a drop of blood on the client’s skin (avoid touching blood or puncture site).
18. Touch and hold the drop of blood to the edge of the sample port until you hear a “beep” (if volume is turned on) and the view window is filled with blood. If the view window is not completely filled with blood the test will not start. If this happens, discard the test strip and repeat with a new GE100 Blood Glucose Test Strip.
19. Countdown mode will begin on the display window. After 5 seconds, test result will appear.
20. Apply cotton ball to client’s finger and ask client to apply pressure at puncture site.
21. Apply bandage to client’s finger at puncture site (if necessary).

22. Discard used lancet into red sharps container. Never reach in or try to remove any material from the sharps container.
23. Record every blood glucose test on study screening form and on client results form. Explain results to client.
24. Discard all other used testing supplies (alcohol prep pad, cotton ball, bib, used test strip, etc.) into trash. Never push down on trash or reach into trash to remove objects.
25. Use alcohol wipes (at least 70% alcohol) to clean and disinfect the GE100 Blood Glucose Monitoring System. Staff should be careful to ensure that the entire meter, including the top, sides, and bottom, are wiped off, while ensuring that “liquid” alcohol is not dripped directly into the electrical components of the meter. The Monitoring Systems should then be allowed to “air dry” prior to being used on the next client.
26. Remove exam gloves by pulling gloves off using the wrist section and inverting the gloves as they are removed from your hands. Dispose gloves in trash.
27. Use hand sanitizer to clean hands.
28. At the end of each screening event and as needed during screening activities, put on a new set of gloves and use Sani-Cloths to sterilize table, pens, glucometers, and all other supplies at testing station.

7.2.2 Performing a Quality Control Test with the GE100 Blood Glucose Monitor

Always follow manufacturer guidelines and instructions when using the GE100 meter. It is necessary to perform a Quality Control (“QC”) Test to ensure the meter is functioning properly.

When to Perform a QC Test:

- If meter is dropped or appears damaged
- When using a new shipment or lot of test strips
- If meter was left out in extreme heat or cold
- If meter was exposed to any liquid (including any cleaning solutions that may have entered meter’s testing port)
- After any confirmed “Hi” or “Lo” test result on a patient
- Whenever test result seems to be an error
- After replacing the meter battery
- Every 2 weeks, if not already preformed for other reasons.

A Quality Control Log should be kept to ensure the QC procedures have been completed at least every 2 weeks (see **Appendix Q**). All QC logs should be saved and stored with other project documents.

Performing a Quality Control Test with the GE100 Blood Glucose Meter

1. Take one GE100 Blood Glucose Test Strip from the vial and close the vial cap immediately.
2. Insert the GE100 Blood Glucose Test Strip with the indication symbol facing up, into test strip port.
3. While the blood drop icon is flashing on the display window, press and hold the Main button for at least 3 seconds until the “CS” symbol appears.

4. You will see the blinking “drop” icon and “CS” icon on the screen, prompting you to apply GE100 Control Solution.
5. Shake the bottle of GE100 Control solution well before opening cap. Place cap on a flat surface.
6. Place a drop of the control solution onto the top of the cap.
7. Gently touch the sample entry of the strip with the GE100 Control Solution from the top of the cap. The screen will display the count time starting from 5 (you will hear a beep if the volume is turned on).
8. Tightly replace the cap on the GE100 Control Solution bottle.
9. The Control Solution result will appear. Compare your Quality Control Test result to the Control Solution Range printed on the GE100 Blood Glucose Test Strip vial label.
10. Record the QC result and any comments on the GE100 Quality Control Log (**Appendix Q**).
11. All QC logs should be saved and stored with other project documents.
12. When a meter fails a QC test, refer to the user manual for troubleshooting steps and then perform a second QC test. If after troubleshooting, a meter still does not pass a QC test, replace the meter.

QC Testing Notes

- Control Solution Test should be conducted between 59-104°F (15-40°C).
- Before the drop icon and “CS” appears, do not touch the GE100 Control Solution to the sample entry on the strip. The GE100 Blood Glucose Meter is performing an internal check. Touching the Control Solution to the sample entry before prompted will result in an error message, drop icon, and beeps (if volume is turned on).
- Do not drip the GE100 Control Solution into the sample port of the strip directly. The reagent on the strip might leak into the bottle of GE100 Control Solution and cause degeneration of GE100 Control Solution. Doing this could also contaminate the meter via the test strip port.
- Do not touch anything to the tip of the GE100 Control Solution bottle.

Maintenance of the GE100 Blood Glucose Meter

Keep the GE100 Blood Glucose Meter and Test Strip free of dust, water, and any liquids. Store the meter in the carrying case when not in use. If meter is dropped or damaged, perform a quality control test with the control solution before doing a blood glucose test.

Cleaning the GE100 Blood Glucose Meter

Clean the outside of the GE100 Blood Glucose Meter with a damp cloth and mild soap/detergent. Do not get the test strip port wet. The meter should be cleaned with 70% alcohol, as described earlier, between client uses.

Cleaning the GE100 Blood Glucose Meter Test Strip Port

If Test Strip Port is stained with blood, control solution or any other liquid, use a dry tissue or cotton swab to clean it immediately. Do not use anything wet to clean it. Perform a quality control test to ensure that the GE100 Blood Glucose Meter is working properly.

7.3 Point-of-care HbA1c testing

We will use the PTS Diagnostics A1CNow®+ System to conduct all point-of-care (POC) HbA1c testing with food pantry clients and study participants. HbA1c testing will be conducted by trained study staff or food bank personnel. Testing will follow manufacturer guidelines for device use, maintenance, storage, cleaning, and quality assurance (see A1CNow®+ System User Guide in **Appendix N**).

Materials List for HbA1c Testing

- A1CNow®+ System Monitor
- A1CNow®+ System Blood Collector, Sampler Body, and Cartridge
- Hand sanitizer
- Nitrile gloves
- Alcohol prep pad (minimum 70% alcohol)
- Single-use lancet device
- Cotton balls
- Bandage
- Dental bib (disposable barrier)
- Surface sanitizer (Sani Cloth Super Wipes)
- Trash can with liner
- Sharps container

7.3.1 Procedure to conduct an HbA1c test

1. Prior to starting an HbA1c test, ensure you have access to a stable, level surface at room temperature and out of direct sunlight.
2. Have client sit at health screening table.
3. Introduce yourself and provide client with background on screening.
4. Ask client: “have you ever been told by a doctor that you have diabetes?”
5. Always maintain client privacy. If necessary, ask other food bank clients to stand away from the screening area.
6. Clean hands with hand sanitizer.
7. Set up supplies. Ensure that lot numbers on Monitor, pouched test Cartridge, and pouched Sampler all match.
8. Put on exam gloves.
9. Ask if client has a preference for which finger to use in order to access blood sample.
 - a. Do not use any site on a finger that is an open wound, has scar tissue, has evidence or infection, or has any other contraindication (e.g., previous diabetes-related amputation, scleroderma); select a different finger for testing.
10. Ask client to hang hand below table and open and close their fist 3-4 times in order to increase blood flow to the fingers.
11. Open alcohol swab and clean finger at site where sample will be obtained.
12. Allow finger to air dry or blot with clean cotton ball to dry site.
13. Open pouched Sampler Body and Blood Collector.

14. Place lancet device against prepared site and push down quickly and firmly. The side of the finger provides a blood sample with less pain than the center of the finger pad.
15. Assess puncture site; if necessary provide light pressure around puncture site to form a drop of blood on the client's skin (avoid touching blood or puncture site).
16. Gently touch tip of Blood Collector to puncture site to completely fill Collector. Wipe away excess blood from Collector (if necessary). A blood sample size of 5 microliters (μL) is required to run a test. A large blood drop is approximately 5 μL .
17. Apply cotton ball to client's finger and ask client to apply pressure at puncture site.
18. Fully insert Blood Collector with sample into Sampler Body.
19. Shake Sampler Body well 6-8 times.
20. Stand Sampler Body on table while preparing test Cartridge.
21. Insert Cartridge into Monitor. Ensure that codes match and Monitor is placed on a level surface, at room temperature, and out of direct sunlight. Sample must be applied to Cartridge within 2 minutes.
22. Wait for "SMPL" to display on Monitor.
23. Remove base of Sampler Body and dispense sample into Cartridge.
24. Do not handle Monitor again until test is complete (approximately 5 minutes).
25. Once test is complete, Monitor will display quality control test result ("QCOK" indicates the Monitor is functioning properly with no detected errors), HbA1c result, and number of tests remaining for Monitor. Refer to User Guide for list of error codes if "QCOK" is not displayed.
26. Apply bandage to client's finger at puncture site (if necessary).
27. Discard used lancet into red sharps container. Never reach in or try to remove any material from the sharps container.
28. Record HbA1c result on study form (screening log and enter in MS Access database at site or immediately after screening event) and on client results form. Explain results to client.
29. Discard all other used testing supplies (used test Cartridge, used Blood Collector and Sampler Body, alcohol prep pad, cotton ball, bib, etc.) into trash. Never push down on trash or reach into trash to remove objects.
30. Remove exam gloves by pulling gloves off using the wrist section and inverting the gloves as they are removed from your hands. Dispose gloves in trash.
31. Use hand sanitizer to clean hands.
32. At the end of each screening event and as needed during screening activities, put on a new set of gloves and use Sani-Cloths to sterilize table, pens, Monitor, and all other supplies at testing station.

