4.2 Study Flow

For a detailed, illustrated overview of the flow of participants through the study, see **Appendix C**. For a general overview that can be used when describing the trial to staff, clinic partners, and pantry agencies, see **Appendix AQ**. An overview of the study flow is below:

1. Screen for diabetes with HbA1c testing
2. Perform informed consent, HIPAA
3. Conduct baseline survey
4. Randomize the participant
5. Perform intervention, wait list intervention
6. Perform follow-up survey and HbA1c testing
7. Provide compensation at baseline and/or at follow-up survey (see **section 9.3**)

Study Approach to Screening and Enrollment

When enrolling new clients into the study, every effort should be made by study staff to complete all enrollment processes (HbA1c testing, consents, baseline survey, randomization, and study orientation) on-site and face-to-face with the new study participant.

If a food bank client is identified as eligible to participate in the study but does not have time to complete these enrollment processes, then study staff should not consent and enroll the client at that time. Instead, study staff should attempt to identify a time and food distribution location occurring within 2 weeks that is available to the client so that they can enroll into the study and complete all enrollment processes during one encounter.

Additionally, for study participants completing their follow-up and /or final HbA1c testing and surveys, study staff should attempt to complete testing and surveys in-person during one encounter.

If necessary, FANO and UCSF project staff can review challenges to this approach identified by the food banks and work to develop alternative screening, enrollment, and survey administration strategies that are responsive to issues identified at the participant / food pantry level. Food bank staff should communicate any screening, enrollment, and survey administration challenges directly to [name], FANO Project Manager.

5 Screening and Eligibility Criteria

To help assure that study sites accrue participants with the required characteristics, this section provides a detailed discussion of the screening procedures, including checking random blood sugar and HbA1c levels, and eligibility and exclusion criteria.

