- Month 5, Week 2
 - Participant receives bi-monthly food box, passive education materials, and 1-on-1 education from food bank staff
- Month 6, Week 1 = T6
 - Participant completes 6-month HbA1c test with study staff
 - Participant completes T6 survey with study staff (CASIC)
 - Participant receives \$30 gift card for completion of survey
 - Participant receives final bi-monthly food box, passive education materials, and 1-on-1 education from food bank staff
 - Participant attends monthly group drop-in diabetes education class
- Month 12 = T12

- Participant completes 12-month HbA1c test with study staff
- Participant completes T12 INT survey with study staff (CASIC)
- Participant receives \$15 gift card for completion of survey
- Participant formally exits research study

Participants – Control Group

- Day 1 (Month 1, Week 1) = T0
 - Food bank client participates in diabetes screening (blood glucose and/or HbA1c testing) event at food pantry; study staff verifies that client meets eligibility requirements for study inclusion
 - Client agrees to participate in study and completes written consent form with study staff
 - Participant completes baseline survey with study staff (CASIC)
 - Participant randomly assigned to study control group by study staff
 - Participant receives \$15 gift card for survey completion
- Month 1, Week 1 – Month 6, Week 2
 - Participant attends regular food pantry distributions and receives normal services per food pantry guidelines (does NOT receive diabetes food packages or education)
- Month 7, Week 1 = T6
 - Participant completes HbA1c test with study staff
 - Participant completes final survey with study staff (CASIC)
 - Participant receives \$15 gift card for survey completion
 - Participant receives 1st bi-monthly food box, passive education materials, and 1-on-1 education from food bank staff
- Month 7, Week 2
 - Participant receives bi-monthly food box, passive education materials, and 1-on-1 education from food bank staff
- Month 8, Week 1
 - Participant receives bi-monthly food box, passive education materials, and 1-on-1 education from food bank staff
- Month 8, Week 2
 - Participant receives bi-monthly food box, passive education materials, and 1-on-1 education from food bank staff
- Month 9, Week 1
 - Participant receives bi-monthly food box, passive education materials, and 1-on-1 education from food bank staff
- Month 9, Week 2 = T9

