13.4.3 Hypotheses

We are testing several hypotheses in this study.

1. The primary hypotheses which we are powered to examine is a significant improvement in HbA1c over a 6-month timeframe.
 - a. For all of these outcomes, we also hypothesize that the effect sizes will be largest among those who completed a minimum amount of exposure to all intervention components. A priori, we defined engagement in the intervention components as: picking up 80% of diabetes-appropriate food boxes, attending the 2 required diabetes education classes, and having at least 1 primary care visit over the 6-month follow-up period.
 - b. We also hypothesized that the intervention would have the largest effect on those in the poorest A1c control (>9%) and those with very low food security status at baseline.
2. Secondary hypotheses: The secondary outcomes of interest are improvements in fruit/vegetable intake, diabetes distress, self-reports of severe hypoglycemic events, depressive symptoms, medication adherence, tradeoffs between affording food vs medication/supplies, food security status, and food stability.
3. Healthcare utilization hypotheses/analyses will be covered in a separate analysis plan

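### At T6 and T12 no rule fixes whether the survey or the HbA1c result comes first; the schedules list the test, with its result explained on the spot, before the self-reported secondary outcomes.

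*Combined protocol and SAP*

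**What the plan says.** **Disclosure.** Section 7.3 names one device "to conduct all point-of-care (POC) HbA1c testing with food pantry clients and study participants", so the procedure in 7.3.1 is not confined to screening. The reading is ready in about five minutes. Step 28 then has staff record it on the study form "and on client results form. Explain results to client".

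**Listed order.** In 9.1 the first T6 item for the intervention arm is "Participant completes 6-month HbA1c test with study staff", and the survey is the next item. The control T6 list and the T12 lists of both arms also put the test before the survey. Appendix E repeats this order.

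**Same visit.** For follow-up, 4.2 says "study staff should attempt to complete testing and surveys in-person during one encounter". Section 7.6.1 puts the survey at about 30 minutes, read aloud by staff.

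**What the survey supplies.** Section 13.4.3 states: "The secondary outcomes of interest are improvements in fruit/vegetable intake, diabetes distress, self-reports of severe hypoglycemic events, depressive symptoms, medication adherence", and the list continues with food-related outcomes. Section 13.4.2 gives the participant survey as the data source besides HbA1c.

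**Order as a safeguard elsewhere.** Sections 6 and 8 require the baseline survey to be finished before the allocation is revealed. Follow-up has no comparable rule: no section asks for the survey before disclosure, holds the result back, or keeps the interviewer from seeing it. Section 6 states that the trial is unblinded.

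**The concern.** HbA1c is the primary outcome. Distress, mood and reported adherence are answers that a fresh HbA1c reading can plausibly colour. If staff follow the order in which the visit items are listed, a participant may hear the reading and then be asked these questions minutes later.

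Both arms are tested and told at T6, so disclosure alone does not favour either arm. The arms separate if the intervention works on HbA1c, because more intervention participants then hear an improved number. Part of a difference in the self-reported outcomes could then be a reaction to that number and not a change over six months. In that case the secondary results would be cited as separate support for a self-management benefit, while being partly an echo of the primary result.

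An order left unstated can also vary between sites and participants, and the analysis could not account for this because the order is not recorded.

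**Working it through.** **1. The plan's own figure (13.4.1).** Inputs: SDs 1.6 and 1.9, correlation 0.51, difference 0.4, two-sided 5% level, 90% power.

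n per arm = (1.6² + 1.9²) × (1 − 0.51²) × (1.960 + 1.2816)² / 0.4² = 299.8, rounded up to 300. The plan's 300 per arm reproduces. These inputs are reused below.

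**2. How far the disclosed news differs between arms.**

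- SD of change = √(1.6² + 1.9² − 2 × 0.51 × 1.6 × 1.9) = √3.069 = 1.752.
- Planned effect in SDs of change = 0.4 / 1.752 = 0.228.
- Assuming no mean change in controls, the share hearing a lower number is Φ(0.228) = 59% in the intervention arm and 50% in controls.

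**3. From news to survey answers.** The documents do not say how far answers shift with a disclosed result. Assumption: a shift of 0.1, 0.2 or 0.3 SD in the survey outcome per SD of HbA1c change. The spurious arm difference is this slope × 0.228.

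**4. Precision.** 720 recruited less 20% leaves 576, or 288 per arm. Carrying HbA1c's correlation over to the survey outcome (a second assumption), the SD multiplier is √(1 − 0.51²) = 0.860 and the standard error is 0.860 × √(2/288) = 0.0717 SD. With no baseline adjustment it is √(2/288) = 0.0833 SD.

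**5. Chance of a significant result when the outcome has no six-month effect.** With q = spurious difference / standard error, the rate is 1 − Φ(1.960 − q) + Φ(−1.960 − q).

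| Assumed slope | Spurious difference (SD) | Rate, correlation 0.51 | Rate, no adjustment |
|---|---|---|---|
| 0.1 | 0.023 | 6.2% | 5.9% |
| 0.2 | 0.046 | 9.8% | 8.5% |
| 0.3 | 0.068 | 15.9% | 13.0% |

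With no HbA1c difference between arms, the spurious difference is zero and the rate stays at 5%.

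**6. Sensitivity to the scale of the assumption.** If the same 0.1 to 0.3 SD applied per percentage point of HbA1c, the spurious difference would be 0.4 × slope, or 0.04 to 0.12 SD. With 300 per arm and correlation 0.51, the rate would be 8.8% to 40%. The result therefore depends mainly on a slope that nobody has measured here.

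**The case against.** The strongest reply is that the order of bullets is not a rule. Item 6 of the study flow in 4.2 reads "Perform follow-up survey and HbA1c testing", with the survey first, and the timeline headings in 2.7 mostly do the same. The schedules look like inventories of a visit: at T3 the test is listed before the food box, and at the control arm's T9 after it. One encounter is an aim, and 7.6 lets surveys be done later or by phone. All of this stands. A reader might infer that every participant answers straight after hearing the result, and the documents do not support that.

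A reader might also infer that the interviewer knows the reading. Section 3.1.4 gives testing to food bank staff or volunteers, and 7.6 gives surveys to research staff. One person may do both, and 14.3 lets volunteers do either, but nothing says that the interviewer sees the result.

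Step 28 is worded for screening, and 3.1.4 points follow-up readings to a staff form (Appendix AU). On-the-spot explanation at T6 is therefore a fair inference from the scope of 7.3, not a follow-up instruction.

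The screening HbA1c also precedes the baseline survey, so disclosure before a survey is not new at T6, and the fix makes follow-up conditions differ from baseline. This matters less than it seems. The baseline result came before allocation and was at least 7.5% for everyone enrolled, whereas the T6 result can differ by arm.

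Glucose monitoring is one of the four intervention components in section 3, so a reaction to one's own number is arguably part of the effect. That is a defensible estimand, but the plan does not state it, and a reaction within minutes is not the six-month improvement hypothesised.

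Finally, self-report in an open-label trial is exposed to knowledge of arm whatever the order. True; the fix removes only one avoidable part.

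**Conclusion.** The follow-up order of survey and HbA1c disclosure is unspecified. The detailed schedules list the less favourable order, and nothing prevents disclosure before distress, depressive symptoms and adherence are reported. That is as far as the documents go.

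Any bias between arms by this route needs a real HbA1c difference. Its size is unknown. The figure of about 6% to 16% instead of 5% rests on three things: an assumed slope of 0.1 to 0.3 SD per SD of HbA1c change, the full planned 0.4-point effect, and HbA1c's 0.51 correlation borrowed for the survey outcome. It also supposes that all participants hear the result before the survey; a mixed order would dilute it.

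A reader might conclude that the secondary outcomes cannot support the self-management claim at all. A possible shift of 0.02 to 0.07 SD under these assumptions does not justify that. The primary analysis and the sample size are unaffected. This is a minor design improvement, worth making because it costs so little.

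**What to change.** In step 28 of 7.3.1, in 9.1 and in Appendix E, state for T6 and T12:

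1. The finger-stick is taken and the reading recorded first, which secures the primary outcome.
2. The survey is then administered.
3. Only then is the result explained and any results form given.
4. The order actually used is recorded.

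Two provisos belong in the same text. Any action that section 10 already requires for a reading or for symptoms is not delayed. A participant who leaves mid-survey is given the result before leaving.

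Where two staff are already present, the interviewer should preferably not be the person who read the monitor.

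The cost is that participants hear their result about 30 minutes later, plus one recorded item on order. No visit, staff member or participant is added.
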